Simple reaction time (SRT) test: Subjects will be assessed by an online-based test (<http://getyourwebsitehere.com/jswb/rttest01.html>). Each volunteer will be instructed to press the mouse button as soon as possible, when a stoplight displayed on a computer screen changes from red to green. During the four first study sessions, each volunteer will be tested at baseline (before administration of melatonin), and once every hour for 8 hours after administration of melatonin, as well as 24 hours after administration of melatonin. For the transdermal study session, the test will be performed at every hour on the first day until 16 hours, as well as at 24 and 48 hours.

Other adverse reactions include pre-specified self-reported symptoms of nervousness, confusion, depressed mood, dizziness, headache, garlic breath and burning sensation from application area (yes/no). Volunteers will also be asked to report additional symptoms of adverse reactions, if any (yes/no + description). Results will be noted in the CRF.

When the subjects are included, a set of baseline demographics data will be recorded in the CRF, including date of birth, ethnicity, weight, height, and BMI.

Subjects/population

Inclusion criteria:

- Healthy female
- 20-40 years old
- BMI 18-30

Exclusion criteria:

- Inability to understand Danish, written or spoken.

- Current use of melatonin or other hypnotics/sedatives
- Current pregnancy (a positive urine-HCG; the subjects will be tested prior to each study session)
- Breast feeding
- Current alcohol or drug abuse (defined as over 5 units of alcohol per day, or any usage of illegal drugs)
- Mental illness (defined as being in medical treatment)
- Serious comorbidity (American Society of Anesthesiologists (ASA) physical status 3-4)
- Participation in other clinical trials less than 1 month prior to current study
- Night-shift work within the last 14 days prior to study
- Planned night-shift work within the study period
- Known and diagnosed sleep-disorder (defined as being in current medical treatment)
- Plasma hemoglobin <7.8 mmol/L (measured when screening participants)

Withdrawal and dropout criteria

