The volunteers can withdraw their consent at any point during the trial. The dropout criteria of the study are if a subject at some point during the study starts to fulfill any of the exclusion criteria, or if a subject is unable to participate in all five study sessions. Furthermore, the investigator can at any point exclude participants from the trial, if the investigator deems it necessary for the safety of the participant. The reason for a subject withdrawing their consent will be reported in the CRF. Data from dropouts will not be used in the statistical analysis.

Conclusion of the study

Each volunteer will have concluded the study after finishing all five study sessions. A total of ten subjects will be included in the study. In case of dropouts, the study will be concluded after a total of eight subjects have completed the study. If more than two subjects drop out, we will include further subjects until a minimum of eight subjects have completed the study.

Handling of melatonin formulations

Storage

Melatonin alcohol/saline solution

Dry melatonin will be packaged according to EU GCP/GMP-guidelines in containers with 25 mg melatonin. All containers with dry melatonin will be given a batch number. The 99.9% ethanol solvent will be packaged in ampoules and also be given a batch number. The melatonin, the 0.9% saline, and the 99.9% ethanol solvent will be acquired via Skanderborg Apotek.

Melatonin rectal fluid

The melatonin fluid, consisting 25 mg of melatonin dissolved in 2.5 mL of a 20% w/w glycofurol, and 40% w/w DMSO solution in water. This fluid has been demonstrated by Bioneer A/S to have no degradation of melatonin while being stored at 25°C for 45 days. Therefore, the fluid will be stored at room temperature. This fluid will be produced and packaged by Glostrup Apotek, according to GMP-guidelines. The fluid will be packaged in single dose mini enemas, and each box will contain 12 mini enemas.

Melatonin/DMSO solution

The melatonin will be dissolved into a 50/50% w/w DMSO and water solution at a concentration of 0.5 mg/g. This solution has been demonstrated by Bioneer A/S to have no degradation of melatonin while being stored at 25°C for 45 days. Therefore, the fluid will be stored at room temperature. The fluid will be packaged in single dose vials (50 ml), and each box will contain 12 vials. The melatonin/DMSO solution will be produced and packaged by Skanderborg Apotek, according to GMP-guidelines.

Melatonin suppository

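### All data from any dropout are left out of the analysis, including completed sessions paired with IV and, read plainly, the reaction that made a subject stop

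*Combined protocol and SAP*

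**What the plan says.** *Withdrawal and dropout criteria* gives two ways to become a dropout. The first applies "if a subject at some point during the study starts to fulfill any of the exclusion criteria". The second concerns attendance and is worded "or if a subject is unable to participate in all five study sessions". The same section allows consent to be withdrawn at any time and lets the investigator exclude a participant for her safety. It then states, without qualification: "Data from dropouts will not be used in the statistical analysis". A reason for stopping is required in only one case: "The reason for a subject withdrawing their consent will be reported in the CRF".

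*Conclusion of the study* adds a replacement rule: "If more than two subjects drop out, we will include further subjects until a minimum of eight subjects have completed the study".

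The exclusion criteria include conditions that can arise during the study: "Current pregnancy (a positive urine-HCG; the subjects will be tested prior to each study session"), "Current use of melatonin or other hypnotics/sedatives" and "Planned night-shift work within the study period".

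Four other places bear on the rule:

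- *Design* fixes the order as intravenous, rectal, intravesical, vaginal, transdermal.
- *Statistics* defines bioavailability, f, from the AUC and dose of one route and of the IV session. It defines no separate pharmacokinetic or safety population and no rule for partial data.
- *Objective* names adverse reactions as part of the aim, and *Secondary outcomes* records them as yes/no symptoms.
- *Adverse events* has reactions and events entered in the CRF and has SAEs and SUSARs reported to the authorities.

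**The concern.** The rule removes two kinds of information for which its reason does not hold.

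**Pharmacokinetics.** A completed rectal session paired with a completed IV session gives a full f value whether or not the woman later attends the transdermal session. The rule also reaches back to sessions done while she was eligible. A positive urine-HCG before session 4, for example, removes three sessions that each followed a negative test.

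**Adverse reactions.** A woman who stops because of a reaction in sessions 1 to 4 cannot take part in all five sessions, so she becomes a dropout. If reaction summaries belong to the statistical analysis, the subject whose reaction mattered most is the one left out. *Statistics* does not say whether they belong, and nothing limits the rule to pharmacokinetic data. With eight to ten subjects, one such case is visible. A reaction in session 5 is normally unaffected, because by then all sessions have been attended.

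**Working it through.** **Inputs from the documents.** Ten are included and eight are needed (*Statistics*). Dropouts beyond two are replaced until at least eight complete (*Conclusion of the study*). IV comes first and transdermal last (*Design*). Four routes have an f value. There is no power calculation and no stated dropout rate.

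**The plan's own figure.** Ten included for eight completers corresponds to 8/(1 − 0.20) = 10. The 20% is implied by two in ten and is not stated as a rate.

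**Assumption for what follows.** Ten start and two drop out, which is the plan's full allowance. This is a scenario, not a forecast.

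**1. f values lost.** Eight completers give 8 × 4 = 32 values. Two dropouts who leave after session s (1 to 4) had 2(s − 1) more.

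| Both leave after session | Values lost | Available | Share lost | n per route if kept (rectal / intravesical / vaginal / transdermal) |
|---|---|---|---|---|
| 1 | 0 | 32 | 0% | 8 / 8 / 8 / 8 |
| 2 | 2 | 34 | 6% | 10 / 8 / 8 / 8 |
| 3 | 4 | 36 | 11% | 10 / 10 / 8 / 8 |
| 4 | 6 | 38 | 16% | 10 / 10 / 10 / 8 |

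Under the current rule n is 8 for every route in every row. In the first row no f value is lost, but two IV profiles are.

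**2. Precision of mean f at the same SD.** The 95% half-width in SD units is t(0.975, n − 1)/√n:

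- n = 8: 0.836
- n = 9: 0.769
- n = 10: 0.715

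If both dropouts had completed the route, the ratio is 0.836/0.715 = 1.17, or 17% wider. If one had, it is 0.836/0.769 = 1.09, or 9% wider.

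**3. Reaction rates.** Let c of the eight completers and r of the two dropouts react, with both dropouts dosed by that route. The rate among all dosed subjects minus the analysed rate is (c + r)/10 − c/8 = (4r − c)/40.

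| c | r | Analysed | All dosed | Analysed rate is |
|---|---|---|---|---|
| 0 | 0 | 0/8 | 0/10 | unchanged |
| 0 | 1 | 0/8 | 1/10 | 10 points low |
| 0 | 2 | 0/8 | 2/10 | 20 points low |
| 3 | 0 | 3/8 | 3/10 | 7.5 points high |
| 3 | 1 | 3/8 | 4/10 | 2.5 points low |
| 3 | 2 | 3/8 | 5/10 | 12.5 points low |

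Exact (Clopper-Pearson) 95% intervals are 0 to 37% for 0/8, 0.3 to 45% for 1/10, and 2.5 to 56% for 2/10.

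If only the reacting dropout had received the route, the difference is (c + 1)/9 − c/8 = (8 − c)/72. That is 11 points at c = 0, 7 points at c = 3, and zero only when all eight completers react. Leaving out a single reactor therefore lowers the analysed rate unless every completer reacts. Also leaving out a dropout who did not react can offset or reverse this.

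**The case against.** The plan set its target at eight completers, without a power calculation, and included ten because it expected dropouts. Analysing completers compares all routes in the same women, which is a coherent choice in a fixed-order crossover. The plan promises no confidence interval for f, so the 17% describes a quantity it does not report. The figures also use the full allowance. With one dropout after session 4 and nine completers, the loss is 3 of 39 values (7.7%), and the half-width is about 7.5% wider (0.769 against 0.715). All of this stands. It limits the pharmacokinetic half to lost precision, but it gives no reason to discard completed pairs when a completers-only summary can sit beside them.

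On reactions, consent withdrawal and safety exclusion are listed apart from the two dropout criteria, so a woman who stops because of a reaction might not be a dropout in the strict sense. This does not remove the problem: she is still unable to take part in all five sessions. It is also true that the CRF keeps her reaction and that SAEs and SUSARs are reported regardless. Neither provision sets the analysed population, and a non-serious reaction that ends participation can still be missing from the results.

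The size of the effect is uncertain. The only DMSO reaction figure in the documents is up to 48%, in interstitial cystitis patients, about 4 of 8 if carried over. At c = 4, one reactor among two dropouts gives 4/8 against 5/10, with no shift. *Adverse reactions of DMSO* also describes these effects as self-limiting, so nothing suggests that stopping because of a reaction would be common.

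**Conclusion.** The concern holds. Followed as written, the rule discards completed IV-paired sessions. On its plain reading it can also remove from a stated study aim the woman whose reaction made her stop.

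For f the cost is precision only. With two dropouts it ranges from no values lost to 16% of them, and normally nothing is lost for the transdermal route. No direction of bias is claimed.

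For reactions, the analysed rate could be up to 20 points low in the worst case assumed, which needs both dropouts and no completer to react. It could also be unchanged, or too high. Dropout unrelated to reactions need not bias it.

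These sizes rest on assumed dropout and reaction counts, and the reaction part rests on reading reaction summaries as part of the statistical analysis. If the rule was meant for pharmacokinetics only, the text should say so. The point is worth correcting because the correction is cheap, not because the study fails without it.

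**What to change.** Replace the blanket sentence with three rules:

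- **Adverse reactions:** report them by route for every subject who received that route, giving the session and the reason for stopping. Record the reason, where given, for every dropout and not only for withdrawn consent.
- **Sleepiness score, reaction time and pharmacokinetics:** use every evaluable session, meaning one not affected by the reason for dropout (sedative use or night-shift work, for example). Compute f for a route in all subjects with an evaluable IV session and an evaluable session for that route, and state n per route. Evaluability is best decided before concentrations are known.
- **Withdrawn consent:** use earlier data only as the consent allows.

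Keep the target of eight completers, and add a completers-only summary so that routes can be compared in the same women.

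The change is to protocol wording and needs no extra visits or samples. Its small cost is unequal n across routes in the main summary and some judgement about which sessions are evaluable.

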Before any studies investigating the radioprotective effects of locally administered melatonin can be undertaken in humans, it is imperative that the pharmacokinetic properties of melatonin are investigated when administered in this way. No previous studies investigating the pharmacokinetics of vaginal, intravesical, or rectal administration of melatonin have been performed [23]. The few studies investigating transdermal administration of melatonin have been insufficient [24-26]; only one study has been able to estimate a $T_{1/2}$, and only in two volunteers [27], and no studies have investigated transdermal bioavailability [23].

Study design

Objective

The aim of the study is to determine the pharmacokinetic properties of, and possible adverse reactions of, melatonin when administered intravenously, rectally, intravesically, vaginally, and transdermally, in healthy female volunteers.

Design

This study is a crossover study, including five individual study sessions investigating five different routes of administration of melatonin. Four of the study sessions (intravenous, rectal, intravesical, and vaginal) will consist of one study day and one plasma sample the following day. The transdermal application will consist of one study day, followed by plasma samples at 24 and 48 hours following application. Between each study session, the subjects will have a washout period of a minimum of 7 days. The study will include a total of ten healthy female volunteers.

The subjects will participate in study sessions in the following order: intravenous, rectal, intravesical, vaginal, and transdermal administration. The study will be concluded after the

48-hour plasma sample after transdermal administration. Should a participant be menstruating at the time of the vaginal administration study session, the session will be postponed for one week.

Study course

Study session 1: Intravenous administration

The melatonin will be administered intravenously, followed by plasma samples over the following 24 hours. The intravenous melatonin will be dissolved in an ethanol/saline solution (2 ml 99.9 % ethanol/23 ml 0.9 % saline) containing 25 mg of melatonin. The infusion of melatonin will be performed over 10 minutes, the infusion rate being 2.5 mL per minute.

Study session 2: Rectal administration

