The suppository will consist of a Witepsol S58 base, containing 25 mg of melatonin. The Witepsol S58 base contains hard fat, polyoxyethylene (25) cetyl stearyl ether and glyceryl ricinoleate [30]. The suppositories will be stored at room temperature. The melatonin will be packaged as single dose suppository in blister packs. The sizes of the blister packs are to be decided. An applicator will possibly be included. The suppositories will be produced and packaged by Glostrup Apotek, according to GMP-guidelines.

Melatonin cream

The cream for transdermal application will consist of 25 mg/g melatonin as well as 150 mg/g DMSO, in a cream base. The dose for each application will be 1 g, and the cream will be packaged in 30 g tubes. The tubes will be stored at room temperature. The cream will be produced and packaged by Glostrup Apotek, according to GMP-guidelines.

Administration

A dose of 25 mg melatonin for local administration has been chosen. This dosage was based on the smallest doses that have demonstrated radioprotective effects in animals [7, 31-33]. The dose has been scaled for humans, taking into account that the effect aimed to achieve should be local, rather than systemic. All administrations of melatonin to the healthy volunteers will be performed by an investigator, except for the vaginal suppository and transdermal cream which will be administered by the subjects themselves.

Study session 1: Intravenous administration

On the day of the study, the intravenous solution will be prepared by an investigator: Two ml of ethanol (99.9%) will be aspirated into a 50 ml syringe. Two ml ethanol will be mixed into a glass of 25 mg dry melatonin, and aspirated back into the 50 ml syringe. Another 23 ml of saline 0.9% will be aspirated into the syringe. The solution will contain 25 mg melatonin in a 4 ml ethanol/46 ml saline solution (1 mg/ml). This solution will then be administered as a bolus through a venous line at an infusion rate of 2.5 ml/minute over 10 minutes. This method for delivering intravenous melatonin has been used in a previous pharmacokinetic study investigating exogenous melatonin administration [5, 34].

Study session 2: Rectal administration

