The number of patients needed for this study is not based on a power calculation. We have decided that 8 subjects are needed to collect information of how the plasma concentrations develop over time. Because of the risk of dropouts, we have chosen to include a total of 10 subjects.

Data will be presented as either mean (SD) or median (IQR), unless stated otherwise.

Data will be analyzed using IBM SPSS Statistics for Windows version 22.0 (IBM Corp., Armonk, NY, USA) and Graph Pad Prism version 7.0 (Graph Pad Software Inc., La Jolla, CA, USA).

Time to maximal concentrations (t_{\max}) and maximal plasma concentrations (C_{\max}) will be assessed directly at the relevant time points. The pharmacokinetic variables: absorption constant (k_a), absorption half-life ($t_{1/2}$ absorption), elimination rate constant (k_e) and elimination half-life ($t_{1/2}$ elimination) will be estimated by “the method of residuals” [57]. Areas-under-the-curve (AUC) of plasma concentrations will be calculated by applying the trapezoidal rule [58]. $AUC_{0-\infty}$ will be estimated as $AUC_{0-8 \text{ hours}} + (C_{8 \text{ hours}}/k_e)$. Bioavailability (f) will be calculated as follows:

$$f = 100 \times \frac{AUC_{0-\infty} (\text{rectal, intravesical, vaginal or transdermal}) \times D_{iv}}{AUC_{0-\infty} (iv) \times D_{\text{rectal, intravesical, vaginal or transdermal}}}$$
 where D represents the dose

administered.

Data monitoring and management

This study will be conducted in compliance with the protocol, the ICH-GCP guidelines and the applicable regulatory requirements. The standard procedures for quality control and quality assurance are followed in compliance with the ICH-GCP guidelines, and investigator/sponsor allows direct access to data/documents for monitoring, auditing, and inspection from both the Danish Medicines Agency (Lægemiddelstyrelsen) and the Good Clinical Practice (GCP)-unit. The GCP-unit will monitor the study. Data will be stored electronically on a secure server until 10 years

after the end of the study, after which all person-sensitive data are deleted. Blood samples will be destroyed after analysis, at a maximum of one year after sampling. A biobank will be created, solely containing these blood samples. Until analysis, the blood samples are kept in a locked freezer at -80°C (with a temperature-alarm) in a locked room at Gastroenheden D, Herlev Hospital. The blood samples will be analyzed with the RIA-technique at Gaslab, Herlev Hospital.

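### The intravenous reference solution is misdescribed: 25 mg in 4 ml ethanol and 46 ml saline is 0.5 mg/ml, not 1 mg/ml

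*Combined protocol and SAP*

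**What the plan says.** The intravenous solution is described in two places in the combined protocol and SAP.

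- **Study course, Study session 1** gives an "ethanol/saline solution (2 ml 99.9 % ethanol/23 ml 0.9 % saline) containing 25 mg of melatonin", infused over 10 minutes at 2.5 ml per minute.
- **Administration, Study session 1** gives the bench steps: "Two ml of ethanol (99.9%) will be aspirated into a 50 ml syringe"; then "Two ml ethanol will be mixed into a glass of 25 mg dry melatonin, and aspirated back into the 50 ml syringe"; then "Another 23 ml of saline 0.9% will be aspirated into the syringe". It summarises the product as "The solution will contain 25 mg melatonin in a 4 ml ethanol/46 ml saline solution (1 mg/ml") and gives it at an "infusion rate of 2.5 ml/minute over 10 minutes".

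Two other sections bear on the point. Under **Storage**, the dry melatonin is "packaged according to EU GCP/GMP-guidelines in containers with 25 mg melatonin". Under **Statistics**, each bioavailability is the dose-normalised AUC of the local route divided by that of the intravenous route, "where D represents the dose" administered.

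**The concern.** The summary sentence contradicts itself: its amount and volume do not give its concentration. It also disagrees with the steps just before it, with the infusion just after it, and with the Study course section.

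The ethanol steps are a lesser, separate problem. Two millilitres are drawn up, and then two millilitres are mixed with the powder and drawn back. This can be read as one aliquot or two, and the 4 ml of ethanol in the faulty sentence lends some support to two.

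The error sits in working instructions. The investigator makes up this dose on the study day, whereas the rectal, intravesical and vaginal doses come as packaged single doses. The syringe named is a 50 ml syringe, so the equipment would not expose a 50 ml preparation. The intravesical session really does use 25 mg in 50 ml at 0.5 mg/ml, so that volume need not look odd to the same team.

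The intravenous AUC and dose form the denominator of all four bioavailabilities. A shortfall in the intravenous dose that is not carried into its D would inflate all four by the same factor. More subjects would not remove that inflation, and comparing the local routes with one another would not reveal it.

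**Working it through.** **Inputs**

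- Melatonin per container: 25 mg (Storage; Administration, Study session 1).
- Composition in the summary sentence: 4 ml ethanol + 46 ml saline, labelled 1 mg/ml (Administration, Study session 1).
- Composition in the Study course section: 2 ml ethanol + 23 ml saline.
- Preparation steps: 2 ml ethanol, mentioned twice, and 23 ml saline (Administration, Study session 1).
- Infusion: 2.5 ml/min for 10 min (both sections).

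**Formulas**

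- Concentration = mass ÷ total volume.
- Dose delivered = concentration × volume infused.
- If AUC is proportional to dose and the intravenous D is entered as 25 mg, the reported bioavailability equals the true one × (25 ÷ dose delivered).

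**Step 1: the plan's own figure.** 25 ÷ (4 + 46) = 25 ÷ 50 = 0.5 mg/ml. The stated 1 mg/ml is not reproduced. At 1 mg/ml, 50 ml would hold 50 mg, twice the amount the sentence names.

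**Step 2: the volume infused.** 2.5 × 10 = 25 ml. Giving 50 ml at that rate would take 50 ÷ 2.5 = 20 min.

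**Step 3: the composition in the Study course section.** 25 ÷ (2 + 23) = 25 ÷ 25 = 1.0 mg/ml. The 25 ml infusion then delivers 25 mg in 10 minutes. This agrees with the label, the container, the saline step and the infusion. The 4/46 pair is exactly double 2/23.

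**Step 4: consequences of each reading,** with the infusion stopped at 10 minutes (25 ml) and the intravenous D entered as 25 mg.

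| Reading | Volume | Concentration | Delivered in 25 ml | Bioavailability factor | A true 10% reads as |
|---|---|---|---|---|---|
| 2 + 23 ml, 25 mg (best supported) | 25 ml | 1.0 mg/ml | 25.0 mg | 1.00 | 10% |
| Two ethanol aliquots: 2 + 2 + 23 ml, 25 mg | 27 ml | 25/27 = 0.926 mg/ml | 23.1 mg | 27/25 = 1.08 | 10.8% |
| Doubled batch: 4 + 46 ml, 50 mg | 50 ml | 1.0 mg/ml | 25.0 mg | 1.00 | 10% |
| Sentence taken literally: 4 + 46 ml, 25 mg | 50 ml | 0.5 mg/ml | 12.5 mg | 25/12.5 = 2.00 | 20% |

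The 10% is an illustrative value, not one from the protocol.

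**Step 5: what removes the bias.** Both inflation factors return to 1.00 if the syringe is emptied, which takes 27 ÷ 2.5 = 10.8 min or 50 ÷ 2.5 = 20 min. They also return to 1.00 if D is entered as the amount actually infused. Correcting D alone would not restore the intravenous plasma concentrations (the primary outcome) or the maximum concentration, because the Statistics section does not dose-normalise them.

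**The case against.** The strongest reply is that the faulty sentence describes a result and is not itself a step. No step tells anyone to draw up 46 ml of saline. The steps, the Study course section, the container size, the infusion and even the 1 mg/ml label all lead to 25 ml, so a careful reader would reach the right dose.

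The ethanol reading can be answered similarly. Drawing the liquid *back* into the syringe implies that it came from there, hence one aliquot, and the Study course section states 2 ml.

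The inflation factors need further departures from the text. The natural meaning is that the whole syringe is given, and the Statistics section already defines D as the dose administered. The factor of 2.00 needs three things together: one container made up to 50 ml, the infusion stopped at 10 minutes with 25 ml left, and D entered as 25 mg. The case report form is not among the documents, so what it captures cannot be judged. There is also no evident safety issue: these readings deliver 12.5 to 25 mg, and the protocol cites intravenous doses of up to 100 mg in adults without adverse reactions.

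Most of this stands, and it limits the weight of the point: a biased result is unlikely, and 2.00 is a remote bound. It does not rescue the sentence, which is wrong on any reading and sits in the instructions for the sole reference dose. Nor does it make the ethanol step unambiguous. The 1.08 route needs only a misreading of that step, adherence to the stated infusion time, and the nominal dose in the formula.

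**Conclusion.** The concern holds. The stated concentration is wrong by a factor of two for the amount and volume given, and the volume contradicts the rest of the protocol. The intended solution is almost certainly 25 mg in 25 ml. Under that reading the planned dose is correct and the bioavailabilities are unbiased.

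The possible effect is a common inflation of all four bioavailabilities by 1.08 or, at the extreme, 2.00. Both figures assume that intravenous AUC is proportional to dose, that exactly 25 ml is infused, and that the nominal 25 mg is used in the formula. Nothing in the documents shows that a wrong dose was planned or given. The sentence should be corrected because the error is certain, it affects the only reference session, and the correction costs almost nothing.

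**What to change.** 1. Replace the summary sentence in Administration, Study session 1 with: 25 mg melatonin in 2 ml ethanol and 23 ml saline (total 25 ml, 1 mg/ml).
2. Reword the preparation steps to say that a single 2 ml ethanol aliquot dissolves the melatonin and is then drawn back into the syringe before the saline is added.
3. Preferably, record the infused volume for each subject in the case report form, so that the intravenous D is the dose actually given, as the Statistics section intends. The protocol describes no such record. If the form already has one, nothing needs adding.

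The cost is one corrected sentence, one clarified step and at most one data field. No extra subjects, visits or samples are needed.
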